7.2 Inform rights and obligations

7.2.1 Rights

Research clinicians introduce research process to participants and their families, and emphasize that participation in the study is voluntary. All participant-related events during the study are informed in time so that participants can decide whether to continue or not. Participants and their families can refuse to participate or withdraw at any time during the study without affecting the participants' own medical care or causing other benefit loss.

7.2.2 Obligations

Insist the principle of voluntary and sign the informed consent form before the study begins. Obey the arrangement of research and

cooperate with the research clinicians. Do not use other drugs without authorization during the study period. If must, please consult the research clinicians before usage and inform after usage.

7.3 Study termination:

If continuing to participate in the study is no longer in the best interests of the participants, the research clinicians will recommend participants to withdraw from the study. If there is a potential risk to the health of participants, the research institution or research clinician can terminate the study after informing the participants and their families.

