The risk factors of dementia are mainly divided into genetics, comorbidity, lifestyle and other factors. Genetic factors include: carrying the ε 4 allele of apolipoprotein E (ApoE) gene (13), triggering receptor expressed on myeloid cells 2 (TREM2) gene(14), clusterin (CLU) gene (15), vascular endothelial growth factor (VEGF) gene (16), beta-secretase 1 (BACE1)(17), insulin degrading enzyme (IDE) gene (18), etc. Comorbidity factors include tension-type headache (19), migraine (20), sensory impairment (21), stroke (22), hypertension (23), hyperlipidemia (24), chronic nephropathy (25), insomnia (26), diabetes (24), hearing disorder (27), etc. Lifestyle factors include: smoking (24), secondhand smoke (28), sedentary behavior (29), bad drinking history (24), less physical exercise and cognitive activities (30), etc. Other risk factors include: living in the rural area (31), old age, low education level (22), sex (AD: female (24); VaD: male (32)), loneliness (33), weakness (34), zoster (35), high dose benzodiazepines (36), pesticides (37), exposure to trace elements (38), low folic acid and vitamin B12 and high homocysteine (39), high body mass index (BMI) (40) or unexpected reduction (41), etc. Protective factors are mainly divided into genetic factors, lifestyle and other factors. Genetic factors include: APOEε2 allele, Toll like receptor 9 (TLR9) gene (42), LDL receptor related protein 1 (LRP1) gene (43), etc. Lifestyle factors include: sports, outdoor activities, labor, social activities, intellectual activities, quitting smoking (44), healthy diet (45), supplement folic acid and vitamin B12 (46), etc. Other protective factors include: living in the urban area (31), high education level (44), high level of thiamine diphosphate (47), cantoness/mandarin bilingualism (48), Tai Chi (49), etc. At present, the research on dementia risk and protective factors is lack of quantitative and objective evaluation indicators, and through certain interventions to further clarify the impact of these factors in dementia. By further defining the risk and protective factors of dementia and regulating them on this basis, it is expected to prevent the onset or delay the progress of dementia.

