3.1 Research content

[figure not shown]
- 1. Through the collection of basic demographic information and clinical data from the multi-center cohort, we will calculate the prevalence and incidence rate of AD, VaD, other dementia (mixed dementia, FTD, DLB, PDD, alcohol dementia, hydrocephalus dementia, post-traumatic dementia, etc.), and update the numbers every 1-2 years.
- 2. To clarify the conversion pattern from normal elderly to MCI and from MCI to dementia. Through the collection and analysis of current medical history, past history, family history, living habits, drug use, physical examination and other information, we will explore the protective and risk factors of dementia and its main subtypes (AD, VaD, Other dementia), including age, gender, education level, rural/urban, marital status, parental dementia history, dietary habbit, blood pressure, drinking, smoking, diabetes, hyperlipidemia, cerebrovascular disease, heart disease, depression, hearing impairment, exercise habits (Tai chi, etc.), dementia specialist influence on patients, occupation, BMI, lifestyle changes, air pollution, head injury, social contact, low-income, and other unknown protective or risk factors. To investigate the role of ApoE gene, especially ApoE in the disease onset and development, and to explore the non-pharmacological interventions For the study purpose we do follow-up every 2 or 3 years.
- 3. By using exome sequencing, GWAS, WGS and other methods, we will search for new mutations of known pathogenic genes (APP, PSEN1, PSEN2) of AD in China, find new pathogenic genes and susceptible genes of dementia and its main subtypes (AD and VaD), and understand their distribution. We will explore the independent and combined effect of susceptibility gene variation on the risk of illness in Chinese AD population, and to obtain the key mutation sites that have a clear relationship with the incidence of AD. We will do regular follow up visits for the FAD members with new mutations of pathogenic genes, and clarify the important role of new mutations of pathogenic genes during the onset and progression of AD.
- 4. We will collect the biofluids (blood, cerebrospinal fluid, urine, etc.) and ¹⁸F-FDG / ¹¹C-PIB PET/MR multimodal imaging data from people with normal cognition, MCI, AD (sporadic and familial) and VaD, and conduct regular follow up. Discover and verify the

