4.1.4 Medication situation

The subject's medication needs to be documented in detail, including the name of the medication for the treatment of cognitive impairment and other diseases, the frequency of administration, and the adherence of the medication. Try to have the subject present a

medical record, drug package or prescription.

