6.2.2 Cerebrospinal fluid sample

Lumbar puncture should be done in the morning. To eliminate the impact of puncture bleeding on the quality of cerebrospinal fluid specimens, the first 1-2 ml of CSF should be discarded. 10ml CSF for biomarker analysis should be collected. Centrifuge within 2 hours after collection (2000 rpm for 10 minutes), then pipette and distribute the supernatant into ten of 1.5ml centrifugal tubes, 1 ml per tube. Centrifugal tubes are immediately stored at a -80°C fridge.

7. Informed consent

In this study, a series of memory and intelligence tests will be performed on participants, and if necessary, auxiliary examination will be arranged to confirm the diagnosis. After that, regular follow-up will be arranged for each person to tract the change of disease status. Participants and their families should be informed that they should sign an informed consent form after fully understanding the research, and should be reminded that participation in the study is voluntary.

According to the current edition of the Declaration of Helsinki, the principle of informed consent will be implemented before protocol procedures are carried out. Information about the research content should be provided in both oral and written form and reviewed by an ethics committee. Subjects, relatives and guardians must have ample opportunity to inquire about details of the study. The informed consent should be in the language and script that subjects or legal representative can fully understand. During the clinical study, subjects can keep abreast of their research information.

Informed consent will be recorded by using a written document approved by the Ethics Committee and signed by the subject and/or legally authorized representative. The written informed consent document will embody the elements of informed consent as stated in the Helsinki Declaration and will comply with local regulations. Informed consent should mainly include the following contents:

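### Section 7.2.2 makes participants seek authorization and consult before using other drugs, although the protocol describes no study drug and records usual medication as data

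*Protocol*

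**What the plan says.** The opening of Section 7 (Informed consent) introduces subsections 7.1 to 7.4 with the words "Informed consent should mainly include the following contents". Within that list, 7.2.2 (Obligations) says "Do not use other drugs without authorization during the study period", and continues: "If must, please consult the research clinicians before usage and inform after usage". It names no subgroup, drug class or exempt prescriber. Under 7.2.1 (Rights), participants and families "can refuse to participate or withdraw at any time during the study without affecting" the participant's own medical care.

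Elsewhere the protocol treats medication as something to observe. In 3.1, item 2, the information analysed for protective and risk factors includes "living habits, drug use, physical examination and other information". Section 4.1.4 asks for detailed documentation of medication, "including the name of the medication for the treatment of cognitive impairment and other diseases", together with frequency and adherence. Table 1 in 3.2.2 collects medication for cognitive impairment at baseline and at follow-up.

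**The concern.** The phrase about other drugs presupposes a study drug against which the rest are judged. That belongs in a drug trial, where co-medication can confound the treatment comparison or raise an interaction risk. In a cohort, what participants take in ordinary care is part of what is being studied, and the useful request is to be told about it.

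Two things are at stake. The first is ordinary care: a participant who follows the clause literally would approach the research clinicians before starting a drug, which could delay treatment. The second is the exposure data. A rule requiring permission can change what people take, and it can discourage them from reporting a drug they took without asking. Either would distort the drug-use information that 3.1 intends to analyse.

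**Working it through.** No arithmetic on effects applies. The check sets the relevant sections against each other.

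**1. Status and reach of the clause.** The lead-in to Section 7 makes 7.2.2 prescribed consent content. Because no subgroup is named, it covers the community population (aged 55 or older, 3.2.1) and the hospital groups in 3.2.2: MCI, FAD, SAD, VaD and normal controls. That is 1 + 5 = 6 groups, a planned 100 thousand subjects (3.2.4) and 68 centres (3.2.5). These figures describe reach only.

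**2. Is there a study drug?**
- Section 2.2 (aim 1) describes a prospective cohort used as a database platform.
- No section names an investigational drug, dose, arm or dispensing visit. Table 1 has no dispensing or drug-accountability item.
- Section 8 sets out risks from neuropsychological testing, lumbar puncture, blood collection and imaging, and none from a drug.
- The randomized trials foreseen in 3.1, item 6, are of non-pharmacological treatment.
- Against this, 10.3 says that the sponsor supplies trial medication free of charge. Nothing else in the protocol supports that statement.

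The absence of a study drug is therefore an inference from the design. It is a strong one, with a single unsupported phrase against it.

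**3. What role does medication have?** It is recorded in detail for cognitive impairment and for other diseases (4.1.4), collected again at follow-up for cognitive impairment (Table 1), and used as an input to the risk-factor work (3.1, item 2). It is an observed variable.

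**4. Rule against role.**

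| Element of 7.2.2 | Needed to record medication? | Fits a cohort observing usual care? |
|---|---|---|
| Authorization for other drugs | No | No |
| Consulting research clinicians before use | No | No |
| Informing them after use | Yes | Yes |

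Only the last element serves the stated purpose.

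**5. How long the rule runs.** Section 3.2.3 gives the study as February 2008 to January 2038 or longer, about 30 years. Section 3.2.2(2) gives follow-up at 1 to 3 years. The document does not define the study period for an individual. If it means time under follow-up, the duty to consult first falls mostly between widely spaced visits, when there is no scheduled contact at which to meet it.

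**6. Size of the effect.** None can be computed. No section shows that a centre applied the rule, that treatment was delayed or that an exposure changed.

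**The case against.** **The wording is loose and may be benign.** The text reads like a translation. It could mean only that participants should not add drugs on their own, and should talk to the research team if they need one. On that reading existing treatment is untouched. The operative verb is consult, which is softer than obtaining clearance. This stands: a reader might infer an absolute ban or a veto over treatment, and the second sentence does not support that. But prior consultation is still listed as an obligation, and no prescription from a treating physician is exempted. If the benign meaning was intended, the text should say so.

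**The protocol is not purely observational.** Section 10.3 mentions trial medication, telephone follow-up in 3.2.2(3) collects adverse reactions, and 3.1, item 6, plans randomized trials that include health products. A reader might therefore state flatly that the study has no study drug, or equally that it has one. Neither is established. What can be said is that none is described. A co-medication rule may suit the randomized trials, but 7.2.2 is not confined to them.

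**Specific exposures.** A reader might go further and argue that particular analyses are compromised, since 2.1 lists "high dose benzodiazepines (36") among risk factors and 3.1 lists "blood pressure, drinking, smoking, diabetes, hyperlipidemia, cerebrovascular disease, heart disease, depression". The first is background literature. Most of the second are conditions or habits, and none is a drug exposure, so any link to drug treatment is the reader's addition. The point rests on drug use being an input in 3.1 and on the recording in 4.1.4.

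**Participants are protected elsewhere.** The right to withdraw in 7.2.1 protects care on leaving. It does not lift the obligation for those who stay.

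**The consent form is not visible.** What participants were actually told is unknown. The finding concerns the protocol's own prescribed content.

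**Conclusion.** The point holds. Section 7.2.2 states a rule that is wrong for the design described: it asks for authorization and prior consultation where only reporting is needed. It is an error in stated text, so an analysis plan could not cure it. The possible consequences are delayed ordinary treatment and altered or under-reported drug exposure. They follow only if the clause is taken literally, and none has been shown to occur. A reader might infer from the reach that harm is widespread. The documents do not support that, since the planned enrolment and number of centres would apply equally to any sentence in the consent content.

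The conclusion rests on two assumptions: that the mention of trial medication in 10.3 is template residue, and that centres carried the wording of 7.2.2 into their forms substantially as written. If a study drug does exist, the larger gap would be that the protocol does not describe it. The change should be made, but it can go with the next amendment.

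**What to change.** - In 7.2.2, replace the two sentences on drug use with a statement that usual care is unrestricted and that participants are asked only to report medication changes.
- Put any co-medication restriction in the separate protocols of the randomized non-pharmacological trials foreseen in 3.1, item 6.
- Delete the words trial medication from 10.3.

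The cost is a consent-text amendment through ethics review at the main and sub units (9.1) and internal ethics approval of each unit's consent statement (9.1.4), across 68 centres. Because Table 1 takes consent at baseline only and the study began in February 2008, an amended form alone would reach only new participants. Those already enrolled need a short written notice as well. No visit, data item or analysis changes.

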7.4 Confidentiality

The records of participants will be kept properly in strict confidence, and only those who obtain authorization can preview the records. The ethics committee and the National Food and Drug Administration inspectors are allowed to review records, but the name, contact information and identification certificates of participants will not appear in the review report.

8. Safety and risk to the participant

8.1 Neuropsychological testing

Participants and caregivers may feel tired, boring or embarrassing about neuropsychological testing. If they still cannot cooperate after being persuaded by the research clinician, they can choose to rest for a while before starting again. any problems of the participants detected by the research clinicians through neuropsychological tests (such as cognitive decline, depression, etc.) might expose the participants to unemployment, loss of medical insurance or other discrimination. Therefore, research clinicians should pay attention to the method of notification and avoid these events.

8.2 Lumbar puncture

The participants may have local discomfort at the lumbar puncture site, as well as back pain, neck stiffness and shoulder pain. The puncture site may appear bruising, swelling or rash, and the dizziness or headache may occur for the participants after lumbar puncture. The risk of other related complications is very rare, including the infections of puncture site, allergies to local anesthetics or disinfectants, and the injury of spinal nerve.

8.3 Blood collection

Slight discomfort, bruising, bleeding or infection at the venipuncture site. Very few participants may faint during or after the puncture.

8.4 Imaging

Participants may be allergic to the contrast agent or have radioactive substance radiation exposure risk during the MRI or PET inspection. Participants with metal implants may experience implant displacement during exposure to magnetic fields. Claustrophobia and anxiety may occur on the participants for lying in enclosed spaces.

9. Ethics

9.1 Setting up internal related committees

Both main unit and sub units are required to pass ethical review. China COAST consists of several committees that work together to conduct research. Details are as follows:

9.1.1 Academic committee

China COAST study is mainly managed by an academic committee consisting of the principle investigator (PI) of main unit, all core members, and the PI of each participating unit. The Academic committee will work with the data management committee and the quality control committee to ensure that the China COAST program is conducted in accordance with the prescribed research design and methodology and will be responsible for the review of research protocol that is related to article writing.

9.1.2 Data management committee

China COAST data can be used by qualified academic or research staff to maximize the value of research data. The data management committee is responsible for managing the storage of data, periodically generating data sets, and accepting supervion by the quality control committee to ensure the completion and accuracy of data. To acquire the China COAST research data, an application must be submitted to the academic committee. After the research application is approved, the data management committee is responsible for extracting and distributing data and data statistics.

9.1.3 Quality control committee

Quality control must be performed in real-time during the data collection phase to ensure that enrolled subjects meet the inclusion and exclusion criteria of the study, identify missing or abnormal items, assess the consistency of longitudinal follow-up, and clarify the status of the subject (continue follow-up or termination). The quality control committee is responsible for reviewing the standardization of collection, transportation, storage and analysis of biological samples; whether the imaging data and clinical information provided by each sub-center meet the requirements of the research program, and if there is any inconsistency, the quality control committee will request the research unit to provide missing or clarify contradictory information. The quality control committee is also responsible for the training of researchers to facilitate the consistency and labeling of the entire study.

9.1.4 Internal ethics committee

Internal ethics committee reviews and approves the written informed consent statements of each participating unit, and provide written statements to the subjects and/or their authorized representatives. The research ethics committee is responsible for reviewing the overall research protocol. If any accident or issue that affects the safety of the subject occurs during the research process, the research unit must immediately report to the research ethics committee. The committee organizes an internal meeting to deal with various issues in a timely manner and keeps records in written form.

9.2 Informed consent

The principle of informed consent will be implemented before protocol procedures are carried out. Information about the research content should be provided in both oral and written form and reviewed by a research ethics committee.

Participants, their relatives, guardians or authorized representatives and study partners must be given ample opportunity to inquire about details of the study. The consent form generated by the investigator must be approved, along with the protocol. Consent forms must be in a language fully comprehensible to the prospective participants and/or their authorized representatives. Informed consent will be documented by the use of a written consent form approved by the REB and signed by the participant and/or an authorized representative. The written consent document will embody the elements of informed consent as stated in the Helsinki Declaration and will comply with local regulations. In any case, participants and their legal representatives should sign an informed consent form after fully understanding the research information. Informed consent signed by each participant must be kept on file by the investigator for possible review by regulatory authorities and/or monitors. The informed consent will cover consent for the study including the genetic research as well. Consent forms will specify that DNA and other biomarker samples including imaging are for research purposes only; the research tests are not diagnostic in nature and participants will not be informed of their test results. The informed consent will specify that Xuan Wu Hospital, Capital Medical University will receive and store research data, MRI data and samples.

10. Quality control

The sponsors and research units of the research should adopt the standard operating procedures established by the quality control committee to ensure the implementation of quality control and quality assurance system of clinical research. The quality control committee verifies all observations and findings in clinical trials to ensure data reliability and to ensure that conclusions from clinical trials are derived from raw data. Quality control must be used at every stage of data processing to ensure that all data is reliable and processed correctly.

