3.2 Research methods

Through the establishment of a national multi-center cognition and aging cohort, this study will collect relevant demographic information and clinical data, biofluid samples, neuropsychological evaluation, imaging examination, blood examination and other comprehensive evaluation of study subjects, so as to study the epidemiology, influence factors, genetics and pathogenesis, diagnostic standards, prevention and control strategies of dementia and its subtypes. The study flow chart is as follows (figure 1):

3.2.1 Inclusion and exclusion criteria:

Community population: age ≥ 55 years, male or female, with consent to participant the study.

Hospital population: subjects are all over 18 years old. Through clinical evaluation, neuropsychological test, imaging examination, blood and cerebrospinal fluid examination, etc, we will comprehensively evaluate the cognitive function and various test measures.

(1) MCI and its subtypes

Inclusion criteria:

- 1) Diagnosis according to 2004 Peterson's MCI criteria.
- 2) CDR = 0.5.
- 3) Memory loss is prominent, and may also be with other cognitive domain dysfunction.
- 4) Insidious onset, slow progress.
- 5) Not reaching the level of dementia.

Exclusion criteria:

- 1) With history of stroke and a neurological focal sign, the imaging findings are consistent with cerebral small vessal disease (Fazekas score ≥ 2 points).
- 2) Other neurological diseases that can cause brain dysfunction (such as depression, brain tumor, Parkinson's disease, metabolic encephalopathy, encephalitis, multiple sclerosis, epilepsy, brain trauma, normal intracranial pressure hydrocephalus, etc.).
- 3) Other systemic diseases that can cause cognitive impairment (such as liver, renal and thyroid insufficiency, severe anemia, folic acid or vitamin B12 deficiency, syphilis, HIV infection, alcohol and drug abuse, etc.).
 - 4) Mental and neurodevelopmental retardation.
 - 5) Contraindications to MRI.
 - 6) Suffering from a disease that cannot be combined with cognitive examination.
 - 7) Refuse to draw blood.
 - 8) Refuse to sign the informed consent at baseline

(2) Sporadic Alzheimer's disease (SAD)

Inclusion criteria:

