5.3 PET

5.3.1 FDG-PET

FDG-PET can detect abnormal brain metabolism in patients with dementia, and should be performed within 1 month before or after neuropsychological examination (with no new vascular disease event). Fasting for at least 6 hours before examination, and fasting blood glucose was measured. Blood glucose levels should be <140 mg / dL (7.8 mmol/L). Image acquisition is completed by radiology department of each center, stored and transmitted in DICOM format, and then image processing is carried out to obtain whole brain and regional standard uptake value ratio (SUVR), and used as location and quantitative indicators of brain metabolic function.

5.3.2 ¹¹C-PIB PET

Amyloid tracer [N-methyl-¹¹C]2-[4'-(methylamino) phenyl]-6-hydroxybenzothiazole (¹¹C-PIB) is the mostly studied and relatively mature Phenothiazine Aβ imaging agent, which is a ¹¹C-labeled derivatives of Thioflavin-T. It can specifically bind to Aβ plaques in the brain of AD patients and is used for positioning and quantitative analysis of Aβ in brain. ¹¹C-PIB PET can differentiate AD and normal patients in the early and middle stages of the disease, reflect the pathological changes of brain tissue, provide more objective data for early diagnosis. Further combined with clinical history, laboratory tests, neuropsychology scale and structural imaging results, it can help improve the accuracy of the diagnosis to guide early treatment. Image acquisition is completed by radiology department of each center, stored and transmitted in DICOM format, and then image processing is carried out to obtain whole brain and regional standard uptake value ratio (SUVR), and used as location and quantitative indicators of Aβ deposition.

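### Section 9.2 requires consent forms to call biomarker and imaging tests non-diagnostic and to withhold their results, while sections 3.2.1 and 7 use such tests for diagnosis and promise participants access to their information

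*Protocol*

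**What the plan says.** Section 9.2 dictates consent-form content: "Consent forms will specify that DNA and other biomarker samples including imaging are for research purposes only". The same sentence goes on: "the research tests are not diagnostic in nature and participants will not be informed of their test results". Section 9.2 gives no exception for a result that matters clinically.

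Other parts of the protocol treat imaging and laboratory tests differently:

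- **Section 3.2.1 (4), VaD.** MRI findings (small infarcts, a Fazekas score of at least 2 for white matter lesions, an MTA score of 0) are inclusion criteria.
- **Section 3.2.1 (3), FAD.** A person is excluded when MRI and laboratory tests fail to support, or rule out, a diagnosis of Alzheimer's disease.
- **Section 7, opening text.** "if necessary, auxiliary examination will be arranged to confirm the diagnosis". It also says: "During the clinical study, subjects can keep abreast of their research information".
- **Section 7.2.1.** "All participant-related events during the study are informed in time so that participants can decide whether to continue or not".
- **Section 7.3.** Where there is a potential health risk, the study can be terminated after participants and families have been told.
- **Section 6.1.3.** Routine blood and urine tests, biochemistry, electrolytes, coagulation, and routine and biochemical CSF tests are listed under body fluid biomarkers.

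**The concern.** Sections 7 and 9.2 both govern consent, and a centre drafting a form cannot honour both as written. One tells participants that their biomarker and imaging results will not be given to them. The other tells them that they can follow their research information and that examinations may be arranged to confirm a diagnosis.

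Two things are at stake. The first is whether participants receive a true description of the tests: a scan that decides whether someone is classed as having vascular dementia is being used diagnostically. The second is participant safety. A centre that follows 9.2 to the letter could see an abnormality on MRI or in routine blood work, exclude the person because of it, and have consent wording that says results are not passed on. Section 9.1.4 has the consent statements of each participating unit reviewed, so centres could resolve the conflict in different ways.

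**Working it through.** No arithmetic applies, because the point depends on no numerical input. The check is to set the texts side by side.

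1. **Which tests does the 9.2 sentence cover?** It opens with DNA and other biomarker samples and adds imaging. The research tests in its second half are most naturally those same tests. Neuropsychological testing and physical examination are not named.

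2. **How far does the term biomarker reach?** Section 6.1.3 puts routine clinical chemistry, blood counts, urine and CSF tests under its biomarker heading, and section 6.2.1 requires blood from each participant. Section 5 schedules MRI and PET at each assessment. In this protocol's own vocabulary, 9.2 therefore extends beyond genotyping and investigational assays to ordinary laboratory results and MRI reports.

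3. **Are those tests non-diagnostic?** Section 9.2 says yes. Section 3.2.1 (4) uses MRI as an inclusion criterion for VaD. Section 3.2.1 (3) uses MRI and laboratory tests to decide whether an Alzheimer's diagnosis is tenable. Section 3.2.1 (5) excludes normal controls on MRI signs of infarction or trauma. Section 7 arranges auxiliary examination to confirm the diagnosis, and Table 1 lists clinical diagnosis as an item at baseline and follow-up. The contradiction is direct.

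4. **Are results withheld?** Section 9.2 says they are. Section 7 says subjects can follow their research information, which conflicts. Sections 7.2.1 and 7.3 point the same way less directly: one concerns events bearing on continued participation, the other termination where there is a health risk.

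5. **Is there an exception elsewhere?** Section 10.4 has out-of-range values verified or re-examined and asks investigators for necessary instructions, without saying to whom. Section 9.1.4 sends safety issues to the research ethics committee. Neither states that a participant is told of a result, and neither is cross-referenced in 9.2.

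6. **Who is covered?** Section 9.2 draws no distinction by group, so it applies to all 100,000 planned participants (3.2.4) at 68 centres (3.2.5). The documents give no rate of clinically relevant findings, so no number affected can be derived.

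**The case against.** The strongest reply is that 9.2 is a conventional sentence about research genetics and exploratory biomarkers. It follows directly on a statement about genetic research. On that reading, the auxiliary examinations of section 7 are clinical work-up, distinct from research tests. Other provisions also protect participants: 7.3 on health risks, 9.1.4 on reporting safety issues, the closing words of the 10.4 sentence on abnormal values, and the requirement in 9.2 itself that consent follow the Helsinki Declaration and local regulations. The consent pages are not in the text supplied, so what participants were told cannot be checked.

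Part of this stands. The intended scope may well be narrow, and the protections are real though none is a rule on disclosing results. But the sentence expressly includes imaging, and the protocol never separates research scans from diagnostic ones: the MRI that decides VaD inclusion is part of the study's own schedule. Since 9.2 prescribes the content of the forms, the defect lies in the protocol whatever the forms say.

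A reader might infer more than the documents support:

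- **That every test result is withheld.** The sentence is tied to DNA, biomarker samples and imaging.
- **That section 8.1 contradicts 9.2.** Its instruction, "research clinicians should pay attention to the method of notification and avoid these events", concerns problems found through neuropsychological tests, which 9.2 does not name. Both can be followed.
- **That study tests are done to find treatable disease.** The exclusion lists name "severe anemia, folic acid or vitamin B12 deficiency, syphilis, HIV infection, alcohol and drug abuse", but only as exclusions. Section 4.1.3 establishes past illness partly from records, and 6.1.3 names no thyroid, vitamin B12, folate, syphilis or HIV assay, although its list is open-ended. That study MRI or routine bloods could reveal an excluding condition is inference, though a modest one.
- **That amyloid PET results are to direct participants' treatment.** The remark in 5.3.2, "it can help improve the accuracy of the diagnosis to guide early treatment", is background on the tracer.
- **That disclosure differing by centre would bias cognitive outcomes.** Nothing in the documents shows this.

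**Conclusion.** The point holds in a bounded form. For biomarker samples and imaging, the 9.2 statement that tests are non-diagnostic is contradicted by 3.2.1 and 7, and its statement that results are not given is contradicted by 7 and, less directly, by 7.2.1 and 7.3. Because 6.1.3 classes routine laboratory tests as biomarkers, the literal reach of 9.2 includes ordinary clinical results and MRI reports, and no exception is written.

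This rests on two readings: that the research tests in 9.2 are those named earlier in its sentence, and that biomarker carries the meaning 6.1.3 gives it. If the sponsor meant only genotyping and exploratory assays, the conflict shrinks to one of drafting, but the text still has to say so. It is not established that any participant was denied a result, or that consent already obtained is invalid. The correction is nonetheless necessary, because two sections governing consent disagree on a matter touching participant safety.

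**What to change.** Reconcile 9.2 with 3.2.1, 6.1.3, 7, 7.2.1 and 7.3:

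- State in 9.2 which tests the non-diagnostic and non-disclosure sentence covers, and whether the routine tests of 6.1.3 are among them.
- Correct the non-diagnostic statement for the MRI and laboratory tests that the protocol uses for diagnosis or eligibility.
- Put one consistent disclosure statement in sections 7 and 9.2, and have it cover people excluded because of a finding.

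The sponsor and ethics committee decide what the disclosure rule is. This review asks only that the sections agree with it.

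The cost is a wording amendment to the protocol and consent forms. Design, sample size and data collection are unaffected. The study began in February 2008 (3.2.3), so the ethics committee would also need to consider what, if anything, to tell those already enrolled.
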